6.2.2 Prohibited medication

Use of the treatments displayed in the below table is NOT allowed after the onset of the prohibition period as indicated in [Table 6-5](#) and [Table 6-6](#). Should administration of one of these drugs during the course of the treatment period be required, study treatment should be discontinued as described in the “Action to be taken” column.

Table 6-5 Prohibited medication

Rationale/Group	Medication ¹	Prohibition period	Action to be taken
Medications with a narrow therapeutic range and potential for increased exposure with QBW251 due to inhibition of CYP1A2:	Theophylline ² Tizanidine	Discontinue treatment at least 1 week prior to Day 1	Discontinue study treatment.
Medications lacking information on metabolizing enzymes:	Pirbuterol	Discontinue treatment at least 1 week prior to Day 1	Discontinue study treatment.
Strong uridine diphosphate glucuronosyl transferase (UGT) inhibitors, which will potentially increase systemic concentrations of QBW251	Mefenamic acid Probenecid Valproic acid	Discontinue treatment at least 1 week prior to Day 1	Concurrent administration must be avoided; discontinue study treatment.
Mucolytics	Acetylcysteine Ambroxol Bromohexine Erdosteine	Discontinue treatment prior to or on Run-In 1.	Concurrent administration must be avoided to ensure reliable assessment of symptoms.
Antibiotics (long-term maintenance) ³	Azithromycin Erythromycin Doxycycline	Discontinue treatment at least 30 days prior to Run-In 1.	Discontinue study treatment.

¹ The medications listed here are prominent examples of the group of medications fulfilling the rationale, but all drugs fulfilling the rationale for exclusion are not allowed (e.g. any mucolytic drug).

² Note that theophylline has to be terminated 7 days prior to Run-In 1 due to stipulations for prohibited COPD medications (Table 6-6) and is listed here for completeness of information only.

³ Most frequently used antibiotics are listed only. However, all long-term systemic antibiotic treatment is excluded, regardless of the drug. For use of short term antibiotics for COPD exacerbations: prior to the study refer to the exclusion criteria 9 and 10, during the study, refer to Table 6-2. Any other use of short term antibiotics prior to the study does not require a wash-out.

Table 6-6 Prohibited COPD-related medications

Class of medication¹	Minimum washout period prior to Run In 1
Long-acting muscarinic antagonists (LAMA) (other than as ingredient of study background therapy)	12 hours for twice-daily LAMAs 24 hours for once-daily LAMAs
Short-acting muscarinic antagonists (SAMA)	6 hours
Fixed combinations of long-acting β_2 agonists and inhaled corticosteroids (LABA/ICS)(other than as ingredient of study background therapy)	12 hours for twice-daily combinations 24 hours for once-daily combinations
Long-acting β_2 agonists (LABA)(other than as ingredient of study background therapy)	12 hours for twice-daily LABAs 24 hours for once-daily LABAs
Short-acting β_2 agonists (SABA) (other than trial rescue medication)	6 hours
Oral phosphodiesterase-IV inhibitor	7 days
Xanthines (any formulation)	7 days
Systemic corticosteroids	30 days
Inhaled corticosteroids (other than as ingredient of study-supplied background therapy)	12 hours
Intra-muscular depot corticosteroids	3 months

¹ This table is not considered all-inclusive. Medications should be assessed for adherence to the indication and other inclusion/exclusion criteria. These medications are also prohibited if administered for other indications. This should be taken in the context of COPD severity as well as planned comparator arms. All these medication listed under Table 6-6 may be permitted for the treatment of a COPD exacerbation during the study except intra-muscular depot corticosteroids If intra-muscular depot corticosteroid treatment is required, the patient should be withdrawn from the study treatment. Medications under Table 6-5 are not permitted and should follow the action as listed in the table.

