6.1 Study treatment

[figure not shown]
The study treatment consists of:

- Investigational drug QBW251 (doses of 450 mg, 300 mg, 150 mg, 75 mg or 25 mg) or matching placebo (450 mg b.i.d. treatment has been discontinued),
- COPD maintenance background therapy consisting of a combination of fluticasone furoate, vilanterol, and umeclidinium, and
- Rescue medication consisting of a short acting beta agonist (salbutamol /albuterol).

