6.2.3 Rescue medication

At Screening and whenever needed thereafter, patients will be provided with a short acting beta agonist (salbutamol 100 μ g or albuterol 90 μ g) inhaler to use as rescue medication on an “as needed” basis throughout the study. Nebulized salbutamol/albuterol is not allowed as rescue medication throughout the trial. No other rescue medication is permitted.

The use of rescue medication (number of puffs taken in the previous 12 hours) will be recorded (once in the morning and once in the evening) by the patient, in the electronic patient diary. The rescue salbutamol/albuterol provided at Screening for use during the study should not be recorded on the COPD related prior concomitant page of the eCRF.

The rescue medication will be supplied to the investigator sites locally by Novartis or provided by the study center and reimbursed by Novartis.

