2.5.3 Handling of missing values/censoring/discontinuations

Since the estimand is related to an effect outside of rescue med intake, spirometry measurements within 6 hours of rescue medication or within 7 days of intake of SCS use will be set to missing. If one of the values contributing to the trough FEV₁ variable is missing at a visit, the remaining non-missing value will be taken as trough FEV₁. If both values are missing, then their trough FEV₁ will be regarded as missing at that visit.

For the primary analysis, only on-treatment data (from date of first randomized dose up to 1 day after date of last randomized dose) will be used as the estimand specifies a hypothetical on-treatment effect. Missing on-treatment data will not be explicitly imputed as the MMRM model implicitly imputes missing data assuming the missing at random (MAR) mechanism.

The imputation procedure(s) related to the trough FEV₁ supportive analyses ([Section 2.5.4](#)) are "jump-to-reference" (J2R) and MAR ([Carpenter et al 2013](#)). The imputations will be based on all available data (i.e. from all scheduled time points) using all covariates as specified in the MMRM. For J2R, only placebo (reference) data will be used. For MAR, data from the same treatment arm will be used for building the imputation model. Imputation of intermittent missing observations before treatment discontinuation will be carried out following a MAR mechanism for all treatment arms. Additional details are provided in [Section 5.7](#).

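### Trough FEV1 taken soon after a non-trial bronchodilator given for an exacerbation stays in the primary analysis, while the same value after the study SABA is removed

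*Protocol*

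**What the plan says.** **Permission.** Footnote 1 to Table 6-6 (Protocol 6.2.2) reads: "All these medication listed under Table 6-6 may be permitted for the treatment of a COPD exacerbation during the study except intra-muscular depot corticosteroids". It continues: "If intra-muscular depot corticosteroid treatment is required, the patient should be withdrawn from the study treatment". No other Table 6-6 class is tied to withdrawal there. The footnote closes with "Medications under Table 6-5 are not permitted and should follow the action as listed in the table".

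**Conflicting lead-in.** The opening of Protocol 6.2.2 covers both tables and says "Should administration of one of these drugs during the course of the treatment period be required, study treatment should be discontinued", as set out in an action column. Table 6-5 has that column. Table 6-6 does not; its only other column is headed "Minimum washout period prior to Run In 1".

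**Meaning of rescue medication.** Protocol 6.1 gives "Rescue medication consisting of a short acting beta agonist" (salbutamol/albuterol). Protocol 6.2.3 specifies an inhaler, rules out nebulized salbutamol/albuterol as rescue, and adds "No other rescue medication is permitted".

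**Data rule.** SAP 2.5.3 says "spirometry measurements within 6 hours of rescue medication or within 7 days of intake of SCS use will be set to missing", and Protocol 12.4.3 has the same rule. All other on-treatment FEV1 enters the MMRM. The estimand (Protocol 12.4.1, SAP 2.5.1) and item (a) of the supplementary analysis (Protocol 12.4.4, SAP 2.5.4) name the same two events. SAP 5.8 has no exclusion for concomitant medication.

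**The concern.** The primary estimand is the effect on trough FEV1 in stable periods, outside episodes of worsening. The plan removes a value lifted by the study SABA because it does not represent a stable trough. The same reasoning applies to a value taken an hour after a non-trial SABA or a SAMA given for an exacerbation, yet that value is kept.

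The SCS rule does not close the gap. Protocol 8.3.9 recognizes mild events managed without systemic therapy and moderate events treated with antibiotics alone. An added drug may also continue after the 7-day SCS window has passed. Inclusion criterion 7 selects patients with recent exacerbations, so such events should be expected.

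At stake is the Week 12 adjusted mean in each arm, and through it the dose-response test and the dose estimated for a 50 mL effect.

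**Working it through.** **1. The passages side by side**

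| Drug taken shortly before spirometry, no SCS within 7 days | Permitted for an exacerbation by the footnote? | FEV1 removed? |
|---|---|---|
| Study SABA inhaler, within 6 h | Yes (rescue) | Yes |
| Nebulized or other non-trial SABA | Yes | No |
| SAMA | Yes | No |
| Added LAMA, LABA or LABA/ICS | Yes | No |
| Added ICS or PDE-IV inhibitor | Yes | No |
| Theophylline | Table 6-6 lists xanthines, but Table 6-5 bars theophylline | Conflict; only by timing if study drug is stopped |

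**2. The plan's power figure reproduced**

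Inputs (Protocol 12.8, SAP Section 3): 854 randomized, 20% dropout, SD 200 mL, one-sided 5%, ratio 2:1:1:1:2. Candidate curves are the nine in SAP 5.7.1.

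- Analysed: 854 × 0.8 = 683.2, that is 195.2 each for placebo and 300 mg and 97.6 for each of the other three doses.
- Method: optimal contrast for each curve, multivariate normal critical value (1.987 by simulation), minimum power over the curves.
- At 50 mL: 81.3% (stated 81%). At 60 mL: 92.1% (stated 92%). The Protocol's eleven curves give 81.7% and 92.3%.

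The sample-size figures are sound.

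**3. Form of the bias**

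Let p be the proportion of patients in an arm whose Week 12 FEV1 is affected, and g the mean difference between the retained value and the stable-period value it stands in for.

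Bias in (QBW251 − placebo) = g × (p_QBW251 − p_placebo), with g = drug gain − exacerbation loss.

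- Equal use in both arms: bias = 0.
- If g is positive and use is higher on placebo, the contrast is diluted.
- If g is negative and use is higher on placebo, the contrast is enlarged.

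**4. Illustration (g and p are assumptions; the documents give neither)**

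- g = 100 mL, use 1 percentage point higher on placebo: 100 × (−0.01) = −1.0 mL, or 1.0/50 = 2% of the 50 mL target.
- g = 150 mL, use 3 points higher on placebo: 150 × (−0.03) = −4.5 mL, or 4.5/50 = 9%.
- Reverse case, gain 100 mL and loss 150 mL, so g = −50 mL, use 3 points higher on placebo: −50 × (−0.03) = +1.5 mL.

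Minimum power at a true 50 mL when the placebo mean is raised by the net dilution (nine curves):

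| Net dilution | Power |
|---|---|
| 0 mL | 81% |
| 1 mL | 80% |
| 3 mL | 77% |
| 4.5 mL | 75% |

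**5. Cost of removing the values instead**

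With extra missing data of 2%, 5% and 10%, minimum power at 50 mL is about 81%, 79% and 78%.

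**The case against.** **The analysis matches the written estimand.** The estimand defines stability by rescue medication and SCS, and the data rule applies exactly those two events. This stands: changing the data rule alone would create a mismatch, so the estimand and supplementary item (a) must change with it. It does not explain why two short-acting bronchodilators are treated differently.

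**Study drug may have to stop.** The 6.2.2 lead-in says so, and efficacy values more than 1 day after the last dose are already excluded. A reader might infer from the footnote that every Table 6-6 class, xanthines included, can be given with study drug continuing. The documents do not support that: theophylline is in Table 6-5 with discontinuation, and for the other classes the lead-in and footnote conflict. The gap exists under the footnote's reading.

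**Table 6-6 washouts are entry rules.** This stands. For SCS the table asks for 30 days, while the analysis and the on-study rescheduling rule use 7. A reader might take the table's windows as the sponsor's own on-study contamination windows; they are not.

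**Direction.** A reader might infer that retention raises placebo FEV1 and shrinks the signal. These drugs are permitted only during an exacerbation, when FEV1 may be depressed, so the net shift could go either way.

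**Size.** A difference of 1 to 3 points at one visit, mostly inside windows of hours and without SCS, is not supported by any figure in the documents. Nor is a gain of 100 to 150 mL on top of LABA/LAMA/ICS. Both are assumptions.

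**Feasibility.** Protocol 6.2.1 requires concomitant drugs to be recorded, and SAP 5.1.3 mentions only start and end dates. Clock times are not shown to be collected.

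**Redaction.** Protocol 8.3.9 is blacked out after it begins to discuss scheduled spirometry, so further scheduling rules may exist. The analysis rules in 12.4.3 and SAP 2.5.3 are readable and contain no further exclusion.

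**Conclusion.** The gap is real. As written, a trough FEV1 affected by a permitted non-trial airway drug is kept as a stable-period value, while one affected by the study SABA is removed. It concerns exacerbations treated without SCS, or drugs continued beyond the 7-day SCS window, and it rests on the footnote's permission governing over the lead-in.

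The stronger statement, that the primary result is biased toward no effect by a known amount, is not supported. Bias needs unequal use between arms, its sign depends on whether drug gain exceeds exacerbation loss, and no usage rate or gain is given. The range of 1 to 4.5 mL, with power falling from 81% to about 80% to 75%, shows only what a net dilution of that size would do. It matters because the stated power at 50 mL is close to the plan's 80% aim. The correction is worth making because it is inexpensive and would be post hoc if chosen after seeing data by arm.

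**What to change.** Make these changes before unblinding, including that of trial-team members at an efficacy interim analysis (Protocol 6.4).

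1. **Estimand and data rule together.** In Protocol 12.4.1 and 12.4.3, SAP 2.5.1 and 2.5.3, and supplementary item (a) in Protocol 12.4.4 and SAP 2.5.4, name use of a non-trial airway drug for an exacerbation as an intercurrent event handled like rescue medication. Set trough FEV1 and FVC to missing when measured within a pre-specified analysis window for the class: for example, 6 h for non-trial SABA and SAMA, and 12 or 24 h for added LAMA or LABA according to dosing frequency. State a window for added ICS and PDE-IV inhibitors, or say why none is needed. If the eCRF holds only dates, write the rule at date level. Keep the 7-day SCS rule. Record the change in SAP Section 4.
2. **Reporting.** Tabulate such use by arm and visit, and report the analysis with these values retained as a sensitivity analysis.
3. **Consistency.** The sponsor must reconcile the 6.2.2 lead-in with the Table 6-6 footnote, and the xanthine entry in Table 6-6 with theophylline in Table 6-5.

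Cost: text edits, one derivation and one table, plus a check of what the concomitant-medication page captures. The downside is a few more missing FEV1 values under the existing MAR assumption; 2% more would leave power at 50 mL at about 81%.

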6.2.3 Rescue medication

At Screening and whenever needed thereafter, patients will be provided with a short acting beta agonist (salbutamol 100 μ g or albuterol 90 μ g) inhaler to use as rescue medication on an “as needed” basis throughout the study. Nebulized salbutamol/albuterol is not allowed as rescue medication throughout the trial. No other rescue medication is permitted.

The use of rescue medication (number of puffs taken in the previous 12 hours) will be recorded (once in the morning and once in the evening) by the patient, in the electronic patient diary. The rescue salbutamol/albuterol provided at Screening for use during the study should not be recorded on the COPD related prior concomitant page of the eCRF.

The rescue medication will be supplied to the investigator sites locally by Novartis or provided by the study center and reimbursed by Novartis.

6.3 Subject numbering, treatment assignment, randomization

6.3.1 Subject numbering

Each subject is identified in the study by a Subject Number (Subject No.), that is assigned when the subject is first enrolled for screening and is retained as the primary identifier for the subject throughout his/her entire participation in the trial. The Subject No. consists of the Center Number (Center No.) (assigned by Novartis to the investigative site) with a sequential subject number suffixed to it, so that each subject is numbered uniquely across the entire database. Upon signing the informed consent form, the subject is assigned to the next sequential Subject No. available.

6.3.2 Treatment assignment, randomization

At Day 1, all eligible patients will be randomized via Interactive Response Technology (IRT) to one of the treatment arms. The investigator or his/her delegate will contact the IRT after confirming that the patient fulfills all the inclusion/exclusion criteria. The IRT will assign a randomization number to the patient, which will be used to link the patient to a treatment arm and will specify a unique medication number for the first package of investigational treatment to be dispensed to the patient. The randomization number will not be communicated to the caller.

The randomization numbers will be generated using the following procedure to ensure that treatment assignment is unbiased and concealed from patients and investigator staff. A patient randomization list will be produced by the IRT supplier using a validated system that automates the random assignment of patient numbers to randomization numbers. These randomization numbers are linked to the different treatment arms, which in turn are linked to medication numbers. A separate medication list will be produced by or under the responsibility of Novartis Global Clinical Supply using a validated system that automates the random assignment of medication numbers to packs containing the investigational drug(s).

Randomization will be stratified by smoking status (current or ex-smoker) and severity of airflow limitation ($FEV_1 \geq 30\%$ to $< 50\%$ and $\geq 50\%$ to $< 80\%$), as assessed at Run-In 1.

The randomization scheme for patients will be reviewed and approved by a member of the Randomization Office.

6.4 Treatment blinding

Subjects, investigator staff, persons performing the assessments, and Clinical Trial Team (CTT) will remain blind to the identity of the treatment from the time of randomization until database lock, using the following methods:

(1) Randomization data are kept strictly confidential until the time of unblinding, and will not be accessible by anyone else involved in the study with the following exceptions: PK analyst, independent statistician and programmer supporting the DMC and, if deemed necessary by the DMC, the DMC members.

(2) the identity of the treatments will be concealed by the use of study treatment that are all identical in packaging, labeling, schedule of administration, appearance, taste and odor.

The randomization codes associated with subjects from whom PK samples are taken will be disclosed to PK analysts who will keep PK results confidential until data base lock.

Unblinding will occur in the case of subject emergencies, in case of a DMC request as an outcome of their evaluation and at the conclusion of the study.

Unblinding of predetermined CTT members will occur at the time of the efficacy interim analysis. The study will then continue under the management of a separate blinded team. In order to maintain the integrity of the study data, separate blinded team members will not have access to any unblinded data. The detailed procedures will be described in a separate charter. The remainder of members including clinical study team, subjects, investigator staff, persons performing the assessments will remain blinded until the final database lock.

6.5 Dose escalation and dose modification

Investigational or other study treatment dose adjustments are not permitted. Dose temporary interruptions are permitted under specific circumstances described in [Section 6.5.1](#).

6.5.1 Dose modifications

Study drug dose temporary interruptions are not permitted unless the investigator considers a temporary interruption is necessary for the treatment of an adverse event (if the adverse event grade is severe and suspected to be related to the investigational study drug should be permanently discontinued as described in [Section 9.1.1](#)).

Any interruption of study medication for more than 5 consecutive days during the treatment period should be discussed with the local Novartis Medical Monitor to review the patient's eligibility to continue in the trial.

The study drug dose interruptions must be recorded in the Dosage Administration Record eCRF.

6.5.1.1 Dose adjustments for QTcF prolongation

In case of QTcF > 500 msec, (or QTcF prolongation > 60 msec from baseline)

- Assess the quality of the ECG recording and the QT value and repeat, if needed.
- Interrupt investigational treatment.
- Determine the serum electrolyte levels (in particular hypokalemia, hypomagnesemia). If abnormal, correct abnormalities.
- If possible, collect a time-matched PK sample on that visit (if not already scheduled/taken per [Table 8-1](#)) and record time and date of last study treatment intake.
- If QTcF confirmed by the Central Reading > 500 msec:
 - Permanently discontinue the investigational treatment.
 - Consult with a cardiologist (or qualified specialist).
 - Increase cardiac monitoring as indicated, until the QTcF returns to ≤ 480 msec.
 - Review concomitant medication use for other causes for QT prolongation (refer to <http://www.qtdrugs.org> for known QT prolonging drugs), and for drugs with the potential to increase the risk of drug exposure related QT prolongation.
 - Check the dosing schedule and treatment compliance.

6.5.2 Follow-up for toxicities

Not applicable

6.6 Additional treatment guidance

6.6.1 Treatment compliance

Study drug compliance should be assessed by the investigator and/or center personnel at all visits. The Investigator or designee will collect, from the patient, the used/unused investigational study drug and packaging at all dispensing visits. Study drug compliance will be assessed from the capsule count (unused medication) and from information provided by the patient and/or caregiver. This information should be captured in the source documentation. The total number of doses of investigational treatment administered since the last dispensing visit should be captured in the source documentation, and the start and end date of investigational study drug and any interruptions of investigational treatment of more than 5 days or any interruption of investigational treatment due to an Adverse Event will be recorded on the eCRF. Patient will also be instructed to report any missing doses of investigational study drug in the eDiary.

The number of puffs of rescue medication inhaled will be recorded twice daily by the patient in the eDiary. The patient will be instructed accordingly at Screening (when he/she is provided with the eDiary and the use of rescue medication is discussed). The use of rescue medication will be reviewed at each visit and data from the eDiary downloaded at each visit. Where necessary, the Investigator will discuss compliance/documentation issues regarding rescue medication use with the patient.

The COPD maintenance background therapy compliance will also be monitored at all dispensing visits and information captured in the source documents at site. Information on the start date, end date and interruptions of more than 3 days or due to an Adverse Event must be captured in the eCRF. Any compliance issues must be discussed with the patient.

The investigator must promote compliance by instructing the subject to take the study treatment exactly as prescribed and by stating that compliance is necessary for the subject's safety and the validity of the study. The subject must also be instructed to contact the investigator if he/she is unable for any reason to take the study treatment as prescribed.

